8.1.2 Time to Wound Closure

The time to wound closure defined as the time from the first treatment to complete wound closure ($\geq 90\%$ reduction in wound surface from baseline for 2 consecutive weeks) will be summarized by treatment and compared using analysis of variance with treatment as the fixed effect. This analysis will be performed for both Observed and LOCF imputed ITT populations

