## 1.6 Rationale for Protocol Amendments

Four subjects were enrolled onto version 2 of the Phase 2 portion of the protocol. Three subjects (1 adult and 2 children) were administered 3e8 per wound daily for 5 days. One adult was administered 6e8 daily for 5 days. There were no signs of immunogenicity, no KB103-related adverse events and the data indicate that 3e8 per wound per administration was an effective dose for wounds 20 cm^2 or less.

Post-dose imaging from these patients clearly indicated that wound morphology and size is a major factor in wound healing as a result of KB103 administration. Wounds that were chronic but recurring based on natural history tended to heal and close completely within 7 to 10 days of KB103 administration. Chronic wounds that were open for a few years showed signs of healing following an initial five consecutive applications but the wound healing process appears to stagnate. These wounds would likely benefit from additional administrations to obtain full closure. Caregivers of the patients currently on trial have requested additional administrations to wounds that have clearly benefited but have not achieved complete wound closure.

Therefore, version 3.1 of the protocol incorporated dosing every 2 to 3 days for two weeks at 2e8 PFU with the option of at-home KB103 administrations, at the discretion of the Investigator.

Five patients were enrolled onto version 3.1 of the protocol. KB103 continues to be well tolerated and wound healing is observed in KB103 administered wounds. Wound healing results of the KB103 treated wounds evaluated to-date continues to show improvement. There is also empirical evidence that repeat administration on the chronic wounds that were retreated in patients that rolled over from the previous portion of the study showed improved healing with complete closure of the wound observed. Therefore, version 4.0 incorporates a 2-cycle approach to KB103 administration with greater flexibility given regarding the number of administrations within each cycle to understand the duration of treatment prior to moving into the Phase 3 Clinical trial.

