## 4 Study Design

### 4.1 Study Overview

This study is an intrasubject comparison of KB103-administered and placebo-administered wounds. Up to three 50 cm^2 areas will be selected for entry: one or two will be selected to receive topical KB103, and one to receive topical placebo.

The primary objective of this study is to evaluate clinical efficacy through digital imaging of wounds. Secondary objectives include an evaluation of change in an Investigator's global assessment and change in patient reported outcomes.

[figure not shown]
Patients will be administered Investigation Product (IP) in two cycles. Cycle 1 starts on Day 1. Up to three 50 cm^2 areas are administered IP (one or two KB103 and one placebo) every 2 to 3 days (to correspond with bandage changes) until wound closure, or up to 3 months. IP is administered to the entire areas, on the wound(s) and on intact skin.

Following this initial dosing period, patients will enter into an observation period in which wounds are monitored at home using a phone imaging app. Upon re-opening and/or expansion of a wound in the KB103 treatment area, patients will be asked to return to clinic or will be treated at home to begin the 2nd cycle of dosing.

The 2nd cycle mimics the first. The same 50 cm^2 areas are administered IP (one or two KB103 and one placebo) every 2 to 3 days until wound closure or up to 3 months. IP is administered to the entire areas, on the wound(s) and on intact skin.

After the 2nd cycle of IP administration, patients enter a second observation period. Patients image their wounds at home using a phone app, and return to the clinic at monthly intervals.

Time to wound closure and duration of wound closure will be evaluated after both the 1st and 2nd cycles. Safety will be monitored throughout the study.

Three additional new patients age 2 and older will be enrolled under this version. Patients from this protocol will be allowed to roll over into Phase 3 study of KB103.

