### 10.5.3 Target Wound Area

Target wound surface area is obtained through on-site and at-home imaging of target areas. Change in area from baseline is evaluated for using a paired t-test for each KB103 target wound vs. control wound.

Time to closure and durability of closure will be assessed after each cycle of administrations.

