6.2 Baseline Definition

In general, baseline is defined as the value closest to, but prior to, administration with either KB103 or placebo.

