8.1.3 Duration of Wound Closure

The duration of wound closure, defined as the time from the complete wound healing to the first reduction in wound surface from baseline to a value below 90%, will be summarized will be summarized by treatment and compared using analysis of variance with treatment as the fixed effect. This analysis will be performed for both Observed and LOCF imputed ITT populations

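### The protocol asks for time to closure and duration of closure after each of the two version 4.0 cycles, but the SAP derives one time and one duration per wound, with no cycle

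*SAP*

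**What the plan says.** **Protocol.** Section 2.1 lists time to closure and duration of closure as primary objectives 1b and 1c. Section 4.1 states: "Time to wound closure and duration of wound closure will be evaluated after both the" first and second cycles. Section 10.5.3 repeats the requirement in the analysis plan: "Time to closure and durability of closure will be assessed after each cycle of administrations". Cycle 2 is built to follow a loss of response. Under sections 4.1 and 5.5, the first observation period (OP 1) ends when a closed wound re-opens or an unclosed one enlarges, and the same areas are then dosed again. One wound can therefore have two closure episodes.

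**SAP.** Section 2.2.1 keeps both endpoints as primary for Phase II. Section 8.1.2 reads: "The time to wound closure defined as the time from the first treatment to complete wound closure", where closure means at least a 90% reduction held for two consecutive weeks. Section 8.1.3 takes duration as "the time from the complete wound healing to the first reduction in wound surface from baseline to a value below 90" percent. Each endpoint is "compared using analysis of variance with treatment as the fixed effect". For area, "baseline is defined as the value closest to, but prior to, administration with either KB103 or placebo" (section 6.2), with no new baseline at Cycle 2. The two cycles appear only in the section 3 version table and the version 4.0 schedule in Appendix 1, not in the objectives or any analysis section.

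**The concern.** The SAP gives each wound one starting date, one closure event and one loss of closure. The version 4.0 design can produce two of each, and the protocol wants both. Two things follow.

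- **Closed in Cycle 1.** The wound's only time and only duration are used up there. If it re-opens and closes again in Cycle 2, the SAP derives no time and no duration for that second episode.
- **First closed in Cycle 2.** The wound's time runs from Cycle 1 Day 1, so it adds together Cycle 1 dosing, an undosed observation period of variable length, and the part of Cycle 2 before closure. The result is neither a Cycle 1 nor a Cycle 2 time to closure.

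At stake is a part of the primary analysis that the protocol specifies and the SAP does not deliver. A long, mixed time could also enter a comparison of means in a study of about 12 to 14 subjects.

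**Working it through.** Neither document gives a figure for these endpoints, so there is none to reproduce. The check compares the two definitions and then does date arithmetic.

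**1. Definitions side by side**

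| Item | Protocol 4.1, 10.5.3 | SAP 8.1.2, 8.1.3 |
|---|---|---|
| Times to closure per wound | one per cycle | one |
| Durations per wound | one per cycle | one, ending at first loss |
| Clock start for Cycle 2 | implied by evaluation per cycle | none stated |
| Area baseline for Cycle 2 | not stated | none stated |
| Cycle in the model | not stated | none; treatment only |

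**2. Time recorded for a first closure in Cycle 2**

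SAP 6.1 counts days inclusively (end minus start, plus 1). Closure on Cycle 2 day t is therefore recorded as:

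recorded time = Cycle 1 length + OP 1 length + t

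Inputs:
- Cycle 1 length: 90 days, the 3-month limit in Protocol section 6.
- OP 1 length: 7 to 90 days. This is an assumption, since Protocol 5.5 says only that it varies.
- t: 14 days, also an assumption.

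Results:
- Short OP 1: 90 + 7 + 14 = 111 days
- Long OP 1: 90 + 90 + 14 = 194 days
- Per-cycle time: 14 days

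Over a wider assumed grid (Cycle 1 of 14 to 90 days, OP 1 of 7 to 90, closure on Cycle 2 day 7 to 90), recorded times run from 14 + 7 + 7 = 28 to 90 + 90 + 90 = 270 days. The ratio to the per-cycle time runs from 111/90 = 1.2 to 187/7 = 26.7.

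**3. Subjects affected**

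Only version 4.0 has two cycles. Protocol 4.1 plans 3 subjects. SAP section 3 reports 12 subjects treated to date, with 2, 4 and 5 under the earlier versions. That leaves 12 − 2 − 4 − 5 = 1 under version 4.0, although the same table shows 3 with details to be determined.

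**4. Effect on the pooled KB103 mean**

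The SAP analyses Phase I through Phase II together. From its section 3 table, KB103 wounds before version 4.0 number 2×1 + 4×2 + 5×2 = 20. Adding 3 version 4.0 wounds gives 23. Suppose one of these has the recorded time above and the other 22 are at 14 days (an assumption):

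- (22×14 + 111)/23 = 419/23 = 18.2 days
- (22×14 + 194)/23 = 502/23 = 21.8 days

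The number of version 4.0 wounds matters little. With one (21 in total) the means are (280 + 111)/21 = 18.6 and (280 + 194)/21 = 22.6. With six (26 in total, two KB103 areas in each of three subjects) they are (350 + 111)/26 = 17.7 and (350 + 194)/26 = 20.9.

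**The case against.** - **The reach is small.** This is an unpowered pilot, and the gap touches one to three subjects. That stands, and it limits the weight of the point.
- **The data are not lost.** A reader might infer that Cycle 2 results vanish. They do not: SAP 6.1 lists all case report form data, and 8.1.1.1 adds a listing of area reductions. What is missing is a derived Cycle 2 time and duration.
- **The long time is not a miscalculation.** It is the true elapsed time from first treatment. That is correct. The fault is that the protocol asks for a different quantity, by cycle.
- **First treatment could mean the first in each cycle.** Nothing in the SAP says so, and its baseline rule gives no Cycle 2 baseline. The SAP was written after a partial analysis of an unblinded study, so this should not be left to interpretation.
- **Earlier versions also re-dosed re-opened wounds.** The version 1.0 and 2.2 schedules in SAP Appendix 1 allow this. But they define no cycles, and the requirement to evaluate per cycle is tied to the two cycles of version 4.0.
- **A per-cycle clock can go wrong.** This has force. Dosing stops at closure, so the two-week confirmation can fall after the last dose. A wound that re-opens to under 10% of its original area would already meet the closure threshold at the first Cycle 2 dose. An analysis of variance also has no value for a wound that never closed. The fix has to deal with all three.

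**Conclusion.** The SAP as written does not deliver a primary analysis that the protocol specifies for version 4.0, and it would time a first closure in Cycle 2 across Cycle 1 and OP 1. This should be corrected, but the numerical effect is modest: about 14 to 18–22 days in the pooled KB103 mean for one such wound. That figure rests on the assumed OP 1 length, closure day and common 14-day value for the other wounds.

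Three stronger readings are not supported.

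- A reader might take the three version 4.0 wounds alone and get means of (14 + 14 + 111)/3 = 46 to (14 + 14 + 194)/3 = 74 days. The SAP plans no such subset analysis of these endpoints.
- A reader might infer that version 4.0 was designed to measure how a second course performs. Protocol 1.6 says that "version 4.0 incorporates a 2-cycle approach to KB103 administration with greater flexibility" in the number of administrations, and gives the aim as understanding the duration of treatment.
- A reader might infer a bias for or against KB103. The documents do not fix the direction, since a wound in either arm could first close in Cycle 2.

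**What to change.** In SAP 8.1.2 and 8.1.3, add for version 4.0:

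1. Derive time to closure and duration separately for each cycle, with the clock for time to closure starting at that cycle's first dose.
2. For Cycle 2, measure reduction against the last wound area before the first Cycle 2 dose, and also show it against the original baseline. Report a wound still closed at that point as such, with no Cycle 2 time to closure.
3. Let the two-consecutive-week confirmation run into the following observation period.
4. Use only Cycle 1 values in the pooled KB103–placebo comparison. Count and report a wound not closed before Cycle 2 starts as not closed, censored at the first Cycle 2 dose. Do not drop it or give it a time that spans OP 1. Because an analysis of variance cannot take a censored time, show the number closed and a Kaplan-Meier summary by treatment beside it.
5. Report Cycle 2 time and duration descriptively, by wound and treatment.

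If the sponsor prefers to analyse Cycle 1 only, the SAP should say so and justify the departure from Protocol 4.1 and 10.5.3.

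The cost is SAP wording and one extra table for at most three subjects. The downside is that Cycle 2 remains descriptive. No dosing or visit changes.

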## 10 Statistical Considerations

Post-screening procedures occur as outlined in the Schedule of Events. The end-of-treatment (or treatment endpoint) is also defined as the last assessment time point for efficacy evaluations in order to handle the issue of missing data that is caused by incomplete data collection or early terminations.

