2.2 Study Objectives Phase II

2.2.1 Primary

- 8) To assess wound closure through post-administration imaging:
 - a. To assess proportion of complete wound closure of B-VEC treated wounds to that of placebo treated wounds at weeks 8, 10 and 12.
 - b. Time to wound closure of a KB103-administered wound relative to a placebo-administered wound
 - c. Duration of wound closure of a KB103-administered wound relative to a placebo-administered wound

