6.3 Handling of Missing Data

Missing data will be handled as outlined below:

- All missing and partial dates for adverse events or for medications received after randomization will be queried for a value. If no value can be obtained, substitutions will be made as detailed in [Appendix 2](#). These substitutions will be used in calculations; however, the actual value recorded on the eCRF will be used in all listings.
- Missing primary endpoints, values after the last non-missing value would be replaced by the last recorded observed value. This is analogous to a last observation carried forward (LOCF) strategy for study discontinuations. For all the other endpoints, the missing values will not be imputed.
- The severity and causality assessment for adverse events cannot be missing. Missing data will be queried for a value.

7 Statistical Analysis Methods

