7.3 Treatment Compliance and Exposure

Exposure summary by treatment group will be presented for the Safety and PP populations. The distribution of subjects by the total number of weeks on therapy (baseline, 8, 10, and 12) will be presented. For the Safety population, the summary of exposure will be based on the actual treatment received.

Treatment compliance is defined as the number of wound treatment doses (KB103 and placebo) received divided by the number of doses expected, ($\times 100$) over the time period defined by the first and last treatment dose dates. Descriptive statistics for treatment compliance and the number and percentage of subjects at least 90% compliant will be presented by treatment group for the ITT, Safety, and PP populations.

8 Efficacy (Proof of Mechanism) Analyses

The study has a complete randomized-block design in which each subject serves as a block to receive all of the treatment conditions. The Phase I/II studies provided at least one pair of target wounds, with one wound being treated with placebo and one wound being treated with KB103. Efficacy measurements are taken multiple times (or repeatedly) over the on-treatment period and off-treatment period from each subject.

All data will be presented using summary statistics or frequency tables, as appropriate, and will be analyzed for superiority comparisons between KB103 and placebo treatments. The description of the sample will be done using summary statistics (n, mean, standard deviation, median, and maximum/minimum) for continuous data and using frequency statistics (counts and percentages) for categorical data. Hypothesis testing, unless otherwise indicated, will be performed at the 5% significance level (1-sided). All P-values will be rounded to four decimal places; P-values less than 0.0001 will be presented as '<0.0001' in all tables. Unless specifically stated, all confidence intervals will be two-sided with 95% coverage.

Efficacy measures collected pre-dosing will be considered as the baseline measurement (defined in [Section 6.2](#)) in this study. For all efficacy analyses, subjects will be analyzed in the group to which they were randomized.

The Sponsor, or their designee, will analyze the data using SAS® Statistical Analysis System Version 9.3 or higher.

8.1 Wound Efficacy Analyses:

8.1.1 Change in Wound Surface Area:

The efficacy analyses will be based on the observed ITT population.

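### Time to closure and duration of closure are compared by ANOVA with no rule for wounds that never close or never reopen; if those wounds drop out, a difference in the share closing or reopening is understated

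*SAP*

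**What the plan says.** SAP 2.2.1 lists three Phase II primary objectives. Two are "Time to wound closure of a KB103-administered wound relative to a placebo-administered wound" and "Duration of wound closure of a KB103-administered wound relative to a placebo-administered wound".

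SAP 8.1.2 starts the clock at first treatment and stops it at a reduction of at least 90% that holds for two consecutive weeks. In SAP 8.1.3 duration is "defined as the time from the complete wound healing to the first reduction in wound surface from baseline to a value below 90" percent. Each time "will be summarized by treatment and compared using analysis of variance with treatment as the fixed effect", in the observed and in the LOCF-imputed ITT population.

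SAP section 8 says that the data "will be analyzed for superiority comparisons between KB103 and placebo treatments", at one-sided 5%. It describes a design in which "each subject serves as a block to receive all of the treatment conditions".

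On missing data, SAP 6.3 says that for primary endpoints "values after the last non-missing value would be replaced by the last recorded observed value". In Protocol section 10 the end of treatment "is also defined as the last assessment time point for efficacy evaluations", and Protocol 10.7 rules out other imputation. Protocol 10.5.3 promises an assessment of both times after each cycle but names no method. Neither document mentions censoring, Kaplan-Meier, a log-rank test, or a value for a wound without the event.

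**The concern.** An ANOVA needs a number for every wound it includes, and the two definitions supply one only after the event has happened. Wounds without the event are to be expected. Protocol 5.5 has a rule for wounds still open at the end of Cycle 1. Protocol 1.6 reports long-open wounds whose healing stalled after five applications, although it also reports complete closure on retreatment.

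If such wounds fall out, each arm is reduced to wounds selected on their outcome. A placebo wound that stays open for the whole study then counts for nothing, although it is strong evidence about time to closure. Two primary objectives would be answered in that subset. The model also names no subject term, although the SAP calls the subject the block.

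**Working it through.** **1. What the rules give each kind of wound**

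| Wound history | Time to closure | Duration | After LOCF |
|---|---|---|---|
| Closes, later reopens | defined | defined | not needed |
| Closes, still closed at last image | defined | undefined | stays closed, so never reopens |
| Never closes | undefined | undefined | stays open, so never closes |
| One closed reading, then lost | two weeks not observed | undefined | can create a second closed week nobody saw |

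LOCF and the protocol's last-measurement endpoint carry a surface value, not an event time. In the last row LOCF manufactures an event.

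**2. Inputs.** The plan states no power or effect size for either endpoint, so there is no figure to reproduce.
- Wounds, from the SAP section 3 table: KB103 2×1 + 4×2 + 5×2 = 20, plus 1 for the twelfth subject (assumed one-to-one) = 21; placebo 12.
- Window of 12 weeks (about the 3-month limit per cycle); one-sided 5%.
- Closure shares q by week 12 and within-subject correlation (0 or 0.5): assumed.

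**3. Size of the difference.** For exponential times, rate λ = −ln(1−q)/12. Mean among closers = 1/λ − 12(1−q)/q. Mean with non-closers counted to week 12 = q × (closers' mean) + 12(1−q).
- q = 0.9: λ = 0.1919; closers 5.21 − 1.33 = 3.88 weeks; all wounds 0.9×3.88 + 1.2 = 4.69.
- q = 0.5: λ = 0.0578; closers 17.31 − 12 = 5.31 weeks; all wounds 0.5×5.31 + 6 = 8.66.
- Difference: 5.31 − 3.88 = 1.4 weeks among closers; 8.66 − 4.69 = 4.0 weeks among all wounds. The first is about 36% of the second.

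With log-normal times (log-SD 1.2) the two differences are 2.5 and 4.8 weeks.

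**4. Power for time to closure** (2,000 simulated trials per cell, exponential times, correlation 0 / 0.5)

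| Assumed closing, KB103 vs placebo | Closers-only ANOVA | Log-rank stratified by subject |
|---|---|---|
| 90% vs 50% | 25% / 24% | 70% / 89% |
| 90% vs 30% | 26% / 27% | 95% / 100% |
| 90% vs 70% | 19% / 17% | 36% / 54% |
| 70% vs 30% | 10% / 10% | 63% / 81% |

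Log-normal times at 90% vs 50% give 55% / 56% against 87% / 98%. A trial with fewer than two closers in an arm was scored as no rejection. With 12 independent placebo wounds at 50% that has probability 13/4096 = 0.3%, so it does not drive the first row.

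**5. Where the loss arises, 90% vs 50%, exponential.** Adding only a subject term to the closers-only ANOVA gives 20% / 48%. Keeping non-closers at 12 weeks, without a subject term, gives 82% / 88%. Both omissions matter: at correlation 0.5 the subject term alone recovers 48 − 24 = 24 of the 89 − 24 = 65 points.

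**6. Duration.** Assume 20 KB103 and 6 placebo closed wounds, independent, 80% of placebo wounds reopening within 12 weeks, and a reopening hazard ratio of 0.33 (41% reopening on KB103). The difference is 1.0 week among reopened wounds and 3.3 weeks when still-closed wounds count to week 12. Power is 12% for the event-only ANOVA and 63% for an unstratified log-rank.

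**7. False positives.** With equal closure (70% or 40%) the closers-only ANOVA rejects in 3.4% to 5.2% of trials. A smaller run of 1,500 trials at 70% gave 6.3% and 2.7% (correlation 0 and 0.5; simulation error about 0.6 points). This shows no clear inflation. With equal reopening medians the duration ANOVA rejects in 1.8% to 4.5%.

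**The case against.** Several stronger readings are tempting, and the documents do not support them.

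- *That the SAP excludes wounds without the event.* It is silent. An analyst could enter the last visit as if it were an event. That keeps most of the power (82% / 88% in step 5) but treats censored times as observed. What stands is that the same data allow two quite different analyses.
- *That any real difference would be understated.* This is conditional. With 80% closing in both arms and faster closure on KB103 (22 and 12 independent wounds), the closers-only difference was 2.73 weeks against 2.18 with non-closers counted to week 12. The closers-only ANOVA then had more power than the log-rank (92% against 31%). Understatement needs a difference in the share of wounds with the event. For closure, that is the SAP's own alternative hypothesis in 8.1.1.
- *That ANOVA fails when few placebo wounds close.* One closer in an arm is enough to compute it; only zero blocks it. At 30% closing that has probability 0.7^12 = 1.4%.
- *That dropped wounds explain nearly all of the loss.* Step 5 shows that the missing subject term also matters when wounds within a subject are correlated. The SAP wording does not, however, rule out a random block.

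It is also fair to say that this is a pilot without a sample-size calculation, and that formal hypotheses are written only for the week 8, 10 and 12 proportion, which counts unhealed wounds and is unaffected. In protocol version 4.0 the first observation period runs until reopening (Protocol 5.5), which eases the duration problem for those few subjects, although Protocol 4.1 ties the trigger to the KB103 area. These points limit the consequence. They do not supply the missing rule.

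**Conclusion.** The point holds and should be fixed. The stated method does not suit the two endpoints: their definitions leave some wounds without a value, and no rule in either document fills the gap. If only wounds with the event are analysed, a real difference is understated whenever KB103 changes the share of wounds that close or reopen. If the shares are equal and only speed differs, it need not be.

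The size is illustrative. Closure and reopening rates, time distributions and within-subject correlation are all assumed, and the twelfth subject's wound count is a guess. The harm is lost power and poor estimates on two primary objectives; it does not make a false positive claim more likely.

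**What to change.** - **Time to closure:** right-censor wounds without closure at their last image, show Kaplan-Meier curves by treatment, and test with a log-rank or Cox model stratified by subject.
- **Duration:** show Kaplan-Meier time to reopening among closed wounds, censored at the last image. Read any comparison as conditional on closure.
- **LOCF:** drop these versions of both analyses.
- **Record:** date and justify the change, because SAP section 1 says that a partial analysis had already been done.

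The cost is SAP wording and standard code, with no new data. Stratifying loses power if wounds within a subject are uncorrelated: 70% against 86% for the unstratified log-rank at 90% vs 50% closing. At correlation 0.5, however, the unstratified test is conservative (it rejects in 1.4% to 2.2% under equal rates), while the stratified test stays near its level (4.6% to 5.5%).

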4.1 Number of Subjects

A formal sample size calculation was not performed for this study. The sample size is based on what was considered an adequate number of subjects for a pilot study to obtain sufficient information on the safety and effectiveness of KB103. Enrolled up to 12 subjects (including Phase I and Phase II).

5 Study Populations

The primary population for an analysis of the proof of mechanism is the intent-to-treat (ITT) population. Study populations are defined in the following sections.

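### The SAP compares time to and duration of wound closure by an ANOVA that names no subject term, although its own design makes each subject a block

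*SAP*

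**What the plan says.** SAP 2.2.1 lists three Phase II primary objectives. The second is "Time to wound closure of a KB103-administered wound relative to a placebo-administered wound" and the third is "Duration of wound closure of a KB103-administered wound relative to a placebo-administered wound".

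SAP 8.1.2 states that the first of these "will be summarized by treatment and compared using analysis of variance with treatment as the fixed effect". SAP 8.1.3 gives the same method for duration: "compared using analysis of variance with treatment as the fixed effect". Neither section mentions a subject, block, repeated or random term.

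The opening of SAP Section 8 describes the design differently: "The study has a complete randomized-block design in which each subject serves as a block to receive all of the treatment conditions". Protocol 4.1 likewise calls the study an intrasubject comparison. SAP Section 8 sets hypothesis tests at 5%, one-sided, unless otherwise indicated.

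The protocol does not fill the gap. Its Section 10.5.3 gives a paired t-test for wound area, but for time to closure and durability it says only that they will be assessed after each cycle.

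**The concern.** An ANOVA with treatment alone is the pooled two-sample t-test. It treats all wounds as independent. Differences between subjects cancel out of the KB103-placebo contrast but stay in the error variance. Where a subject has two KB103 wounds (protocol versions 2.2 and 3.x), those two are also treated as unrelated.

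Positive correlation is plausible, because wounds on one subject share a genotype, caregiver, bandage schedule and supportive care. Protocol 6.3 also asks for similar locations where possible. The main statistical gain of an intrasubject design would then be lost on two primary objectives in a trial of about 12 subjects, and a real effect on speed or durability of closure could be missed.

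This is separate from how the analysis treats wounds that never close or never reopen. It would remain if every wound closed and reopened.

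**Working it through.** **1. Is there a plan figure to reproduce?** No. SAP 4.1 and protocol 10.1 say that no formal sample size calculation was done, and neither document gives a correlation, SD, effect size or power. The only stated figure is the one-sided 5% level. In simulation the unpaired test keeps that level (4.8% to 5.1%) when wounds on one subject are uncorrelated.

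**2. Inputs.**
- Subjects: 12 (SAP 4.1; the protocol synopsis allows up to 14).
- Wounds, from the table in SAP Section 3: 2 Phase I subjects with one KB103 wound each; 4 + 5 = 9 subjects with two; the twelfth is assumed to have two. KB103 wounds: 2×1 + 10×2 = 22. Placebo wounds: 12.
- Assumed, not in the documents: normal outcomes with SD 1, equal correlation rho between wounds on one subject, and a value for every wound.

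**3. Variance of the treatment difference.** The treatment-only ANOVA takes it as 1/22 + 1/12 = 0.1288. The true value is

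(1-rho)(1/22 + 1/12) + rho[10(2/22 - 1/12)² + 2(1/22 - 1/12)²] = 0.1288(1-rho) + 0.0034 rho.

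At rho 0.5 this is 0.0644 + 0.0017 = 0.0661. The ratio is 0.0661/0.1288 = 0.513, so the standard error is overstated by 1/sqrt(0.513) = 1.40. When every subject has the same number of KB103 wounds, one or two, the second term vanishes and the factor is exactly 1/sqrt(1-rho), which is 1.41 at rho 0.5.

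**4. Large-sample size of the nominal 5% test.** This is 1 - Phi(1.645/sqrt(1-rho)): 3.3% at rho 0.2, 1.0% at rho 0.5 and 0.13% at rho 0.7.

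**5. Simulation at 12 subjects.** Treatment-only t-test (34 - 2 = 32 degrees of freedom) against a model with subject as a fixed block (34 - 12 - 1 = 21), both one-sided 5%:

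| rho | Size, no block | Size, block | Power at 0.75 SD, no block | Power at 0.75 SD, block |
|---|---|---|---|---|
| 0 | about 5% | about 5% | 64% | 63% |
| 0.2 | about 3.3% | about 5% | 67% | 73% |
| 0.5 | 1.3% | 5.0% | 72% | 89% |
| 0.8 | 0.1% | 4.8% | 79% | >99% |

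The power loss also depends on the effect size:
- rho 0.5: about 24, 17, 5 and 1 points at 0.5, 0.75, 1.0 and 1.25 SD.
- rho 0.2: at most about 6 points.
- rho 0.8: about 58 points at 0.5 SD and 21 at 0.75 SD.
- rho 0: no loss; the block costs about 1 point.

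**6. Other layouts, at rho 0.5 and 0.75 SD.** With 11 subjects power is 67% against 86% (19 points). With 14 it is 79% against 93% (14 points). With 12 subjects and one KB103 wound each it is 58% against 79% (21 points).

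**7. Random instead of fixed subject effect.** With placebo values missing at random, so that 8 or 5 of 12 subjects have one, rho 0.5 and 0.75 SD, power was 56% or 42% without a subject term and 76% or 59% with a random one. The size of the random-subject test was 6.2% or 4.7% (Monte Carlo standard error about 0.6 points). It may therefore run slightly high without a small-sample correction.

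**The case against.** **The SAP does not say that treatment is the only effect.** It says the fixed effect, in a section that opens by calling subjects blocks, so an unnamed random subject term is not strictly excluded. A reader might infer that the plan deliberately discards the pairing; the text does not prove that. The context still favours the treatment-only reading: SAP 8.1.1 stratifies the CMH test by time point and not by subject, and 8.1.1.1 uses the unpaired Wilcoxon rank-sum test. On either reading the term needs to be stated.

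**A single size and power loss cannot be quoted as fact.** A reader might infer that the test simply runs at about 1.4% and loses about 18 points. Those values arise near rho 0.5 and 0.75 to 0.8 SD, and neither input is in the documents. This objection stands in full; only a range is supportable.

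**The test direction is unclear.** An ANOVA F-test has no direction, and the SAP does not say how its one-sided rule applies to it. Run as an ordinary 5% F-test, the size at rho 0.5 with 12 subjects and one KB103 wound each is about 0.9%.

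**Not every wound will have a value.** A wound that never meets the 90% criterion has no closure time and no duration. The main figures do not allow for this, and the missing-at-random runs do not mimic it, because such wounds are missing for not having closed.

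**The consequence is limited.** This is a pilot with no power target. Explicit hypotheses are written only for complete wound healing. Two of the 12 illustrated subjects are Phase I subjects, for whom SAP 2.1.2 makes these endpoints secondary. This supports a moderate grade, but the correction is still worth making.

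**Conclusion.** The point holds as a mismatch between the named method and the stated design. For two of the three SAP Phase II primary objectives the analysis names no subject term, and no other section supplies one. Followed literally, the comparison is unpaired. With positive within-subject correlation its intervals are about 1/sqrt(1-rho) too wide and its test is conservative.

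The size is illustrative. Over rho 0.2 to 0.8 the actual level runs from about 3.3% down to 0.1%, and the power loss from almost nothing to more than 50 points, depending on rho and the effect. All of this assumes 12 subjects, normal outcomes, a value for every wound and a one-sided t-test. The blocked figures in the main comparison come from a fixed-subject model.

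A reader might also infer that the omission threatens a false efficacy claim. It does not: under positive correlation the fault lowers the false-positive rate. The risk is a missed effect. The change should be made, but it is not critical.

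**What to change.** In SAP 8.1.2 and 8.1.3, specify an ANOVA with one record per wound, treatment as a fixed effect and subject as a block. The block may be fixed, or random with a small-sample degrees-of-freedom correction such as Kenward-Roger. A random block keeps wounds from subjects in whom only one treatment has a value. Report the within-subject KB103-placebo difference with its interval, and state how the one-sided level applies.

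If the method is changed to handle wounds that never close or reopen, carry the same block into it, by stratifying on subject or with a subject frailty.

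The cost is one sentence in each section and one model term, with no new data or patients. The downside is the degrees of freedom used by a fixed block (about 1 power point if wounds are truly uncorrelated), or approximate degrees of freedom in the mixed model.
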